1.0 STUDY SYNOPSIS

The purpose of this study is to collect human breath samples for use in a validation study intended to demonstrate equivalent clinical performance measures of new ABCA2 GIRMS instruments to the currently FDA-approved ABCA GIRMS system. ABCA-GIRMS systems are used to analyze the ratio of $^{13}\text{CO}_2$ to $^{12}\text{CO}_2$ in patient breath samples collected during the GEBT test procedure.

In this study the participants will be administered the FDA-approved GEBT test, which involves collecting breath samples prior to and after consumption of a non-radioactive, carbon stable isotope (^{13}C) labeled test meal. Breath samples will be collected at times consistent with FDA approved labeling. Participant's breath samples will be analyzed on the currently approved ABCA GIRMS and on new ABCA2 GIRMS instruments. Resulting DOB values (delta over baseline: difference between pre-meal and post-meal $^{13}\text{CO}_2$ to $^{12}\text{CO}_2$ ratios) and kPCD values ($^{13}\text{CO}_2$ excretion rate (min^{-1}) primary GEBT metric) will be recorded. The DOB and kPCD values will be used to determine the clinical diagnostic agreement at each individual time points and percent agreement in diagnosis between the approved ABCA GIRMS and the new ABCA2 GIRMS.

2.0 DEFINITIONS

| Term/Abbreviation | Definition |
|--|---|
| Carbon-13 | Carbon-13, denoted as ^{13}C , is a stable, non-radioactive , safe, naturally occurring form of carbon. Carbon-13 occurs in nature in a natural abundance of approximately 1%. |
| Carbon-12 | Carbon-12 (^{12}C) is the most abundant, non-radioactive form of carbon in nature. Natural abundance is approximately 99%. |
| ABCA GIRMS | Automated Carbon Breath Analyzer Gas Isotope Ratio Mass Spectrometer. Used to analyze stable, non-radioactive isotopes of carbon, ^{13}C and ^{12}C , in QC gases and human breath samples. The ABCA GIRMS is an FDA-approved instrument for use with Cairn Diagnostics' ^{13}C -Spirulina Gastric Emptying Breath Test ("GEBT"). For these purposes, the instrument measures the ratio of $^{13}\text{CO}_2$ / $^{12}\text{CO}_2$ in QC gases and human breath. |
| ABCA2 GIRMS | Sercon's new model Automated Carbon Breath Analyzer-2 Gas Isotope Ratio Mass Spectrometer. Used to likewise analyze the ratio of $^{13}\text{CO}_2$ / $^{12}\text{CO}_2$ in QC gases and human breath. |
| AE | Adverse Event |
| Delta values ($\delta^{13}\text{C}$) | Amount of ^{13}C in a sample expressed as a ratio of carbon-13 to carbon-12: $\delta^{13}\text{C}(\%) = \frac{R_B - R_S}{R_S} * 1000$ Where R_B is the ratio of $^{13}\text{C}/^{12}\text{C}$ of the sample and R_S is the ratio of $^{13}\text{C}/^{12}\text{C}$ in Pee Dee Belemnite (PDB), the reference standard for these measurements. |

| Term/Abbreviation | Definition |
|-------------------|---|
| DOB | Delta Over Baseline i.e. the difference in delta value at any given time point and the pre-meal/baseline delta value. Used in kPCD calculations. |
| GEBT | Gastric Emptying Breath Test. The ¹³ C-Spirulina Gastric Emptying Breath Test ("GEBT") is an FDA-PMA approved, Class III combination drug medical device in vitro diagnostic product intended for measurements of the rate of solid phase gastric emptying and identification of gastroparesis (delayed gastric emptying). |
| GES | Gastric Emptying Scintigraphy |
| kPCD | 1000 x Percent Dose (of Carbon-13) Excreted, ¹³ CO ₂ excretion rate (min ⁻¹) primary GEBT metric |
| PHI | Personal Health Information |
| SAE | Serious Adverse Event |
| WOCBP | Woman of Childbearing Potential |

3.0 BACKGROUND

3.1 Intended Use

The Gastric Emptying Breath Test (GEBT), to be used with the GEBT test meal, is a quantitative test intended for use in the measurement of the rate of gastric emptying of solids and to aid in the diagnosis of delayed gastric emptying (gastroparesis) in adults who are symptomatic for gastroparesis. For these purposes, the test system utilizes a Gas Isotope Ratio Mass Spectrometer (GIRMS) for the measurement of the ratio of ¹³CO₂ to ¹²CO₂ in breath samples.

The GEBT should be administered under supervision of a health care professional although no specialized facilities or specially licensed personnel are required.

Note: The addition of the new ABCA2 GIRMS system as a component of ¹³C-Spirulina GEBT will not change the intended use of GEBT. The new ABCA2 GIRMS instruments are intended to serve the same analytical function and use the same analytical platform and analytical methodology as the original ABCA-GIRMS to determine the ratio of ¹³CO₂ to ¹²CO₂ in human breath samples.

3.2 Principle of the GEBT

After an overnight fast, a test meal containing non-radioactive ¹³C-labeled Spirulina is administered to the patient. As the test meal is emptied from the stomach it is rapidly absorbed across the duodenum and metabolized giving rise to exogenous ¹³C-labeled CO₂ which is excreted in the breath. The rate of ¹³CO₂ excretion in breath at any given GEBT measurement time is directly proportional to the rate of gastric emptying.

3.3 Description of the GEBT Device

Cairn's ¹³C-Spirulina GEBT is a Class III in vitro diagnostic medical device that consists of three FDA regulated components:

- A diagnostic drug (¹³C-Spirulina/Egg mix) that contains the active pharmaceutical ingredient (¹³C-Spirulina) that gives rise to ¹³C-labeled CO₂ in patients' breath when taking the test.

- A kit containing the diagnostic drug, repackaged saltine crackers, consumables used to prepare the meal, a breath collection kit (screw capped glass tubes and a straw), materials to allow return of breath samples and approved labeling (instructions for use/package insert).
- An Automated Breath Carbon Analyzer Gas Isotope Ratio Mass Spectrometer (ABCA-GIRMS) used to determine the ratio of $^{13}\text{CO}_2$ to $^{12}\text{CO}_2$ in breath samples.

3.4 Components and Pictures of ^{13}C -Spirulina GEBT Kit, Prepared Test Meal and ABCA GIRMS Instruments

The components of the ^{13}C -Spirulina GEBT are addressed below.

- ^{13}C -Spirulina Gastric Emptying Breath Test (GEBT) – Test Meal (^{13}C -Spirulina/Egg)

Ingredients: Desugared whole eggs, Dry non-fat milk solids, Salt, Smoke Flavoring (Char Oil), ^{13}C -labeled Spirulina

Nutritional value: Fat 8.8 g; Carb 4 g; Fiber 0 g; Protein 12g
 Energy value; 150kCal
 Net weight; 27g
- ^{13}C -Spirulina Gastric Emptying Breath Test (GEBT) – Saltine Crackers (3 packages of 2 crackers)

Ingredients: Unbleached enriched wheat flour (wheat flour, niacin, reduced iron, thiamine mononitrate, riboflavin, folic acid), canola oil, palm oil, sea salt, malted barley flour, baking soda, yeast.
 Nutritional value; Fat 1 g; Carb 14 g; Fiber 0 g; Protein 1g
 Energy value; 80 kCal
 Net weight; 18 g
- Overall Meal Nutritional/Energy Values
 Fat 9.8g, Carb 18g, Fiber 0g, Protein, 13g, 230kCal

Table 1. Contents of ^{13}C -Spirulina GEBT Kit

| Meal preparation components of Kit | Breath Sample Collection Components of Kit |
|---|---|
| 1 Instructions for Use/Package Insert | 1 Test Request Form |
| 1 ^{13}C -Spirulina/Egg Meal packaged in a foil pouch with oxygen absorber | 2 Blue-Capped Exetainer tubes labeled for pre-meal collection |
| 3 packages of 2 saltine crackers re-packaged in a foil pouch with oxygen absorber | 6 White-Capped Exetainer tubes labeled for post-meal collection |
| 1 large (~13 fl oz/390 mL) microwaveable cooking cup | 2 drinking straws |
| 1 filling cup (small (~3.5 fl oz/~100 mL) plastic cup with pour spout for transferring water) | 1 Breath tube holder |
| 1 plastic cutlery kit (knife, fork and spoon) | 1 Pre-labeled Bubble Mailer |

Figure 1. Contents of ^{13}C -Spirulina GEBT Kit Displayed

Figure 2. Prepared ^{13}C -Spirulina GEBT Test Meal and Breath Sample Collection Components

Figure 3. ABCA GIRMS instrument Currently Approved by FDA for Use with GEBT

[figure not shown]

Figure 4. New ABCA2 GIRMS instrument

3.5 Summary of Relevant Clinical Studies

The GEBT was validated in FDA-approved dual-labeled validation studies. The comparative method was a nuclear medicine procedure known as Gastric Emptying Scintigraphy

("GES"). GES is conducted by administering a radionuclide-labeled test meal to a fasting patient and measuring the rate of radiation decline with time as the stomach empties the labeled test meal. In the validation studies GEBT and GES were conducted concurrently (Mayo Clinic). GEBT demonstrated excellent agreement with diagnosis by GEBT vs. GES.

The FDA approved GEBT for commercial use in April 2015 (Pre-Market Approval PMA P110015: Gastric Emptying Breath Test). Exhibit A includes the FDA's public announcement of the approval and a copy of PMA 110015 Gastric Emptying Breath Test Letter of Approval.

GEBT has an excellent safety profile with no serious adverse events reported in pre-validation, validation and post validation studies. There have been no medical device reportable (MDR) events post approval (> 5,000 GEBT).

A recent international consensus statement recommended GEBT for use in the evaluation of gastroparesis "because of its careful validation, high concordance with scintigraphic data and FDA approval" (INTERNATIONAL CONSENSUS STATEMENT: Advances in the diagnosis and classification of gastric and intestinal motility disorders. Gastroenterology and Hepatology, Volume 15, May 2018).

GEBT is currently used in the majority of Phase II, and III pharmaceutical studies for new drugs for gastroparesis. In these studies, GEBT is used to identify gastroparetic patients for enrollment and to assess physiologic effects of new pharmacologic agents (U.S.

Department of Health and Human Services, Food and Drug Administration, Center for Drug Evaluation and Research (CDER); Gastroparesis: Clinical Evaluation of Drugs for Treatment; Guidance for Industry. July 2015, August 2019. Clinical/Medical).

Table 2 below summarizes key peer-reviewed literature regarding ¹³C-Spirulina GEBT.

Table 2. Summary of Key Peer-Reviewed Literature

| Publication | Brief Description |
|---|--|
| J S Lee, M Camilleri, A R Zinsmeister, D Burton, L J Kost, P D Klein. A valid, accurate, office based non-radioactive test for gastric emptying of solids Gut 2000;46:768–773 | Proof of principle study in healthy subjects showing the excellent correlation of simultaneous ¹³ C-Spirulina GEBT measurements with GES. |

PRO-CD-039, ABCA2 GIRMS Analytical Validation Precision Study – Patient Sample Collection, was designed to collect human breath samples for use in a validation study intended to demonstrate equivalent analytical precision of new ABCA2 GIRMS instruments to the FDA-approved ABCA GIRMS system. In this study, the participant's breath samples were analyzed on the FDA-approved ABCA GIRMS and on the new ABCA2 GIRMS instruments. The resulting delta ($\delta^{13}\text{C}$) values ($^{13}\text{CO}_2$ to $^{12}\text{CO}_2$ ratios) and DOB values (delta over baseline: difference between pre-meal and post-meal $^{13}\text{CO}_2$ to $^{12}\text{CO}_2$ ratios) were recorded and used to calculate within and between instrument precision performance characteristics for the ABCA GIRMS systems.

PRO-CD-042, ABCA2 GIRMS Analytical Validation Interference/Specificity Study – Patient Sample Collection was designed to collect human breath samples for use in a validation study intended to demonstrate comparable performance characteristics of new ABCA2 GIRMS instruments to the FDA-approved ABCA GIRMS system. In this study, the participants had breath samples collected prior to and after administration of a potential interfering substance that were identified in the original validation of the ABCA GIRMS system or identified as possibly present in breath samples in the ABCA2 GIRMS risk assessment. The samples were analyzed on either the ABCA2 GIRMS (all identified potential interferences) or the FDA approved ABCA GIRMS (newly identified potential interferences). The resulting delta ($\delta^{13}\text{C}$) values ($^{13}\text{CO}_2$ to $^{12}\text{CO}_2$ ratios) were recorded and used to determine the interference/specificity of the ABCA GIRMS systems.

4.0 STUDY GOALS AND OBJECTIVES

The purpose of this study is to collect human breath samples for use in a validation study intended to demonstrate equivalent clinical performance of new ABCA2 GIRMS instruments to the current FDA-approved ABCA GIRMS system. The clinical performance data will be used as part of a supplement submission to FDA demonstrating that both ABCA2 GIRMS systems are suitable for use with GEBT and that the safety and efficacy of GEBT is not affected.

5.0 SUBJECT SELECTION

Cairn personnel and their family and friends may volunteer to be a participant in this study.

Participants may also be recruited from clinical trial sites that have a population that is known to have a history of possible gastric emptying issues (intended use population for GEBT).

This study requires a minimum of seventy-five (75) and up to one hundred and twenty (120) participants.

5.1 Inclusion criteria

Participants are eligible to be included in the study if they meet the following criteria:

- Males and females, 18 – 85 years old at time of signing the informed consent form from healthy and intended use population participants (i.e. symptomology of gastroparesis). Women of childbearing potential (WOCBP) must not be pregnant at the time of GEBT administration.
- Ability to eat test meal and provide breath samples

5.2 Exclusion criteria

- History or physical exam suggestive of pathophysiologic disorders such as renal failure, chronic heart disease, chronic respiratory disease, liver disease, or malabsorption syndrome
- History of abdominal surgery except appendectomy
- Use of any medications that may alter gastric motility within two days of the study
- Use of narcotics or anticholinergics within two days of the study
- Females on hormone replacement therapy other than birth control medications
- Receipt of an investigational drug within 4 weeks of the study
- Pregnancy
- Intolerance or allergy to any component of Gastric Emptying Breath Test meal
- History of neurologic or psychiatric disorders

5.3 Participant Meal and Dietary Restrictions

Participants will fast for at least 8 hours (preferably overnight) prior to administration of the GEBT and during the GEBT (with the exception of eating the test meal). Alcohol should not be consumed within 8 hours prior to testing. Participants may consume a small amount of water up to 1 hour before the test, but not more than 4 fl oz.

Subjects should not smoke/use tobacco products (e.g. chewing tobacco, nicotine gum) before or during administration of the GEBT.

5.4 Participant Activity Restrictions

Participants will abstain from strenuous activity for at least 8 hours prior to administration of the GEBT. Participants may participate in light activities during administration of the GEBT (e.g. watching television, reading, using restroom) but otherwise will remain comfortably seated in the test administration location.

6.0 STUDY PROCEDURES/RESEARCH METHOD

6.1 Study Scheme

Visit 1: For each potential participant, perform a screening visit at a GEBT trial site where the study is explained to the participant. Ensure that the participant is eligible to participate in the study. Answer any questions about the GEBT test procedure and ask the participant to provide consent to participate in the study (See SPEC-CD-035, Informed Consent). Participants are free to leave the test site upon completion of the screening visit.

Visit 2: Within two weeks of visit 1, participants will return to the GEBT test site at which time the GEBT will be administered. After confirmation that the participant has met the fasting and dietary restriction requirements, the participant will provide a baseline (PRE-meal) breath sample by exhaling into two blue-capped glass Exetainer tubes. The participant will then consume the prepared GEBT test meal. After consuming the test meal, post meal breath samples will likewise be collected at 45, 90, 120, 150, 180 and 240-minute timepoints.

Visit 3: Follow up contact (e.g. phone call, email, in-person, etc) will be made with the participant within one week following the GEBT administration to assess whether there are any post-administration adverse events and to complete subject's participation in the study.

Table 3. Schedule of Activities (SoA)

| Procedure | Screening (Visit 1) | Visit 2 | Follow-up (Visit 3) | Notes |
|---|------------------------|------------|------------------------|-------|
| Informed Consent | X | | | |
| Inclusion and Exclusion Criteria | X | | | |
| Administration of ¹³ C-Spirulina GEBT | | X | | |
| AE review | | | X | |
| SAE review | | | X | |

6.2 Handling and analysis of breath samples

The handling and analysis of breath samples collected by this protocol is fully described in PRO-QC-202, ABCA2 GIRMS Clinical Performance Measures (Exhibit B). In summary, human breath samples collected will be analyzed on the original ABCA GIRMS system. The samples will then be analyzed on either the ABCA-C or ABCA-D ABCA2 GIRMS systems and then analyzed a third time on the ABCA2 GIRMS system on which the breath samples have not been analyzed.

6.3 End of Study

The participant is considered to have completed the study when they have completed the GEBT test administration and all collected breath samples have been analyzed on the approved ABCA GIRMS and two new ABCA2 GIRMS systems.

The end of the study is defined as the date on which the analysis of all the participant's breath samples have been completed on the GIRMS systems.

7.0 RISK/SAFETY INFORMATION

7.1 Established Contraindications, Warnings and Precautions of GEBT

The following contraindications, warnings and precautions have been established for the ¹³C-Spirulina GEBT in FDA-approved labeling:

- Individuals with known hypersensitivity to Spirulina, egg, milk or wheat allergens should avoid the GEBT
- Because the GEBT is an indirect multi-compartmental method of measuring gastric emptying, GEBT results may be inaccurate in individuals compromised with significant small bowel, pancreatic, liver, and/or lung disease. Consequently, GEBT should not be administered to patients with pulmonary dysfunction (e.g. COPD) and/or small bowel malabsorption.
- Individuals with severe lactose intolerance may wish to avoid the GEBT, as the test meal contains a small amount of lactose, approximately 2.7 grams.
- The performance characteristics for individuals under the age of eighteen (18) years have not been established for this test.
- The performance characteristics for pregnant women have not been established for this test.
- False positive and false negative results can occur with this test.
- Follow the directions for collecting breath samples carefully. Errors in the timing and/or procedures for collecting breath samples may affect test results and necessitate retesting.
- The GEBT should not be performed in individuals who have taken medications known to influence the rate of gastric emptying (e.g. erythromycin, metoclopramide, opiates and anticholinergics) within three (3) days prior to testing. Individuals should stop such medications only after consulting with and obtaining approval from their attending physician or the physician ordering the test.

| | |
|---|-----------------------|
| CAIRN DIAGNOSTICS | DOC No. PRO-CD-044.01 |
| PRO: ABCA2 GIRMS Analytical Validation Clinical Performance Study – Patient Sample Collection | Page 14 of 22 |

- Fasting serum glucose levels of diabetic subjects should be checked before administration of GEBT and the test should only be administered to subjects with a fasting serum glucose level of <275mg/dl.
- After 24 hours there is no residual $^{13}\text{CO}_2$ signal in the breath arising from the ^{13}C label contained in the GEBT meal; thus, the GEBT may be administered as frequently as every 24 hours.
- The GEBT should not be administered within 24 hours (or the relevant washout period) of other ^{13}C breath tests (e.g. the ^{13}C -Urea breath test for *H. pylori*).

7.2 Potential Risk to Participant Associated with this Study

This study involves the following risks:

- Allergic reactions such as rash, itching, hives or problems breathing are a possibility if the participant were unknowingly and severely allergic to the GEBT test meal ingredients. The ingredients are 100 mg Spirulina, 27 grams of dried scrambled eggs (with nonfat milk added), saltine crackers (containing wheat) and water.

Any unanticipated problems will be reported to the IRB within ten (10) calendar days of being reported.

8.0 MONITORING AND REPORTING OF ADVERSE EVENTS/SERIOUS ADVERSE EVENTS

An Adverse Event (AE) is any untoward medical occurrence in the participant associated with administration of GEBT, whether or not considered related to GEBT.

A Serious Adverse Event (SAE) is defined as any untoward medical occurrence that:

- Results in death
- Is life-threatening
- Requires inpatient hospitalization or prolongation of existing hospitalization
- Results in persistent disability/incapacity

AE's will be reported by the participant (or, when appropriate, by a caregiver, a surrogate of the participant or the participant's legally authorized representative).

The investigator and any qualified designees are responsible for detecting, documenting and recording events that meet the definition of an AE or SAE and remain responsible for following up with AEs that are serious, considered related to the GEBT test procedure or study procedures that caused the participant to discontinue the study.

8.1 Time Period and Frequency for Collecting AE and SAE Information

All AEs or SAEs will be collected from the day of each GEBT test administration until the follow-up visit as outlined in Table 3, Schedule of Activities.

In the event any serious adverse events are reported, or observed during the GEBT administration procedure, whether or not attributable to the GEBT test procedure, the event will be reported within 24 hours to the IRB and to Cairn's medical director.

The following information will be provided in writing: study protocol number, patient's identification code, date of birth, date and nature of the serious adverse event and the causality assessment. The report of an SAE will be completed and signed by the next working day.

8.2 Intensity of an Event

The intensity/severity of an event will be classified as follows:

- Mild: that is an awareness of sign or symptom, but easily tolerated
- Moderate: that is discomfort of sign or symptom, but easily tolerated
- Severe: at least partially incapacitating (or restricting usual activity)

8.3 Relationship to Study Procedures

Adverse events will be considered associated with the study procedure if the attribution is possible, probable or very likely. The relationship can be classified as follows:

- Not related: an adverse event that is not related to the study procedure
- Doubtful: an adverse event for which an alternative explanation is more likely
- Possible: an adverse event, which might be due to the study procedure
- Very likely: an adverse event which is listed as a possible adverse reaction and cannot be reasonably explained by an alternative explanation
- Unknown: it is not possible to assign the reaction to any of the above categories because of insufficient, pending or contradictory information

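### The adverse event schedule, causality scale and severity scale do not match the text that relies on them; they need reconciling so that test-day events are recorded at the time and graded consistently

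*Combined protocol and SAP*

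**What the plan says.** **Timing.** Section 8.1 states: "All AEs or SAEs will be collected from the day of each GEBT test administration until the follow-up visit as outlined in Table 3". In Table 3 (Section 6.1), GEBT administration is marked at Visit 2, while AE review and SAE review are marked only at Visit 3. Visit 3 is a contact within one week of the test, whose purpose is "to assess whether there are any post-administration adverse events and to complete subject's participation in the study".

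**Causality.** The Section 8.3 rule reads: "Adverse events will be considered associated with the study procedure if the attribution is possible, probable or very likely". The list that follows has five grades: *Not related*, *Doubtful*, *Possible*, *Very likely* and *Unknown*. The two lowest are worded "Not related: an adverse event that is not related to the study procedure" and "Doubtful: an adverse event for which an alternative explanation is more likely". The highest is "Very likely: an adverse event which is listed as a possible adverse reaction and cannot be reasonably explained by an alternative explanation". *Unknown* is for events that cannot be placed in another grade because the information is insufficient, pending or contradictory.

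**Severity.** Section 8.2 defines the middle grade as "Moderate: that is discomfort of sign or symptom, but easily tolerated". Mild is awareness of a sign or symptom and carries the same tolerance wording. Severe begins at partial incapacity or a restriction of normal activity.

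**Completion.** Section 6.3 says "The participant is considered to have completed the study when they have completed the GEBT test administration" and the samples have been analysed on all three instruments. It does not mention the Visit 3 contact.

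**The concern.** The protocol has one exposure per participant, at Visit 2. The only risk named in Section 7.2 is an allergic reaction to the meal, and breath collection continues to 240 minutes after it. A site that builds its visit worksheet from Table 3 would find no prompt to record adverse events on that day. Non-serious events might then be captured only from what the participant recalls at follow-up.

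The two scales raise a separate problem. An assessor who thinks an event is probably related has no grade that says so. One who selects *Unknown* cannot tell from Section 8.3 whether the event counts as associated. One faced with an event that is hard to tolerate but not limiting has no severity grade that fits. Different sites could resolve these cases differently.

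At stake is the consistency of the safety record for 75 to 120 participants. No planned analysis result is at stake.

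**Working it through.** No formula applies, and the documents give no figure to reproduce. The check sets each operative statement beside the table or scale on which it depends.

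**1. Section 8.1 against Table 3**

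| Row in Table 3 | Visit 1 | Visit 2 (test day) | Visit 3 |
|---|---|---|---|
| GEBT administration | – | X | – |
| AE review | – | – | X |
| SAE review | – | – | X |

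Safety-review rows marked on the test day: 0 of 2. Marked at follow-up: 2 of 2. Section 8.1 therefore cites a schedule that does not show the test-day collection it describes. The interval to the next scheduled review is up to 7 days (Section 6.1, one week).

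**2. Section 8.3 rule against Section 8.3 scale**

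| Grade | In the rule as associated? | Defined in the scale? |
|---|---|---|
| Not related | no | yes |
| Doubtful | no | yes |
| Possible | yes | yes |
| Probable | yes | **no** |
| Very likely | yes | yes |
| Unknown | **not mentioned** | yes |

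Of the 3 grades that make an event associated, 2 can be recorded and 1 cannot. Of the 5 defined grades, 1 has no explicit treatment. A literal reading leaves *Unknown* outside the associated group, but the text does not say that this is intended.

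The missing grade has little effect on the related/unrelated split. An event that would have been graded *Probable* would most likely be entered as *Possible* or *Very likely*, and both already count as associated. The loss is mainly in grading. *Unknown* is the more direct way for an event to be left out of the associated group.

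**3. Section 8.2 severity grades**

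| Grade | Symptom descriptor | Tolerance or function descriptor |
|---|---|---|
| Mild | awareness | easily tolerated |
| Moderate | discomfort | easily tolerated |
| Severe | – | partial incapacity, or normal activity restricted |

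Two of 3 grades share the tolerance descriptor, so only awareness versus discomfort separates them. An event that is not easily tolerated and does not restrict activity meets none of the three definitions. This is an overlap plus a gap, not a strict contradiction.

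**4. Where the effect stops**

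The acceptance criteria in Exhibit B (agreement at each timepoint and overall) and Exhibit C (bias and total analytical error in DOB) use no adverse event data. None of the above can change them.

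**The case against.** The best reply is that the governing text already closes most of these gaps.

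- **Detection.** Section 8.0 makes the investigator and designees responsible for detecting, documenting and recording events. Section 8.1 itself starts collection on the test day, and SAEs reported or observed during administration go to the IRB and the medical director within 24 hours, whatever their cause. A reader might infer from the blank Visit 2 cells that related events, including a serious allergic reaction on site, would be missed. The documents do not support that. What remains is narrower: non-serious test-day events have no scheduled prompt, and the Visit 2 text in Exhibit D adds none.
- **Follow-up.** A reader might infer that a non-serious *Unknown* event drops out of follow-up, because Section 8.0 ties the investigator's duty to serious, related or discontinuation-causing events. Section 8.4 answers this: after an initial AE or SAE report the medical director follows the participant at later contacts, with no causality condition.
- **Non-allergic events.** A reader might infer that these can never exceed *Possible*, because *Very likely* needs a listed reaction and Section 7.2 lists only allergic ones. Section 8.3 does not say which list it means, and *Possible* is already associated.
- **Regulatory claim.** A reader might infer that the Section 4.0 claim about GEBT safety is undermined. That section rests the claim on clinical performance data, and every participant takes the same approved test whichever instrument later reads the samples.
- **Severity.** Awareness and discomfort do differ, and intensity triggers no action in the protocol.
- **Expected volume.** Section 3.5 reports no serious adverse events in earlier studies and no reportable device events in more than 5,000 tests, so counts are likely to be small.

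These replies limit the consequences. They do not remove the mismatches in Table 3 and in Sections 8.2 and 8.3.

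**Conclusion.** The inconsistencies are real and sit in text that sites will use. Table 3 does not show the test-day collection that Section 8.1 attributes to it, Section 8.3 relies on an undefined grade and is silent on *Unknown*, and Section 8.2 has an overlap and a gap. The schedule mismatch matters most, because it concerns what is written down on the only exposure day.

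The effect is limited to the completeness and grading of the safety record, and the number of events affected cannot be estimated from the documents. It would be wrong to conclude that serious events will go unreported, that the related count will be materially distorted (no such count is a planned analysis in Exhibits B or C), or that the equivalence conclusion is at risk.

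The difference between Sections 6.1 and 6.3 on when participation is complete is a minor administrative point. Section 6.3 does not cancel the Visit 3 contact, and no analysis set is defined by completion.

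Two assumptions underlie this. Table 3 is taken as printed; its consent and administration marks fall under the expected visits, so the column alignment looks sound. The recall risk also assumes that some sites work from the table more than from Section 8.1.

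**What to change.** 1. **Table 3:** mark AE review and SAE review at Visit 2 as well as Visit 3, so that the table agrees with Section 8.1 and non-serious test-day events are recorded that day.
2. **Section 8.3:** make the rule and the scale use the same grades, either by defining *Probable* in the scale or by deleting it from the rule. State explicitly how *Unknown* counts. Treating it as associated until resolved is one convention, but the documents do not dictate it, so the sponsor should choose and write it down.
3. **Section 8.2:** reword *Moderate* so that it no longer repeats the tolerance wording of *Mild* and leaves no gap below *Severe*.
4. **Sections 6.1 and 6.3:** for tidiness, align the completion wording on the Visit 3 contact.

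The cost is two table marks, a few lines of text, matching CRF entries and the IRB submission that Section 13.1 requires for any amendment. Staff already meet participants at each breath collection, so no visit is added. Recorded or associated events may rise slightly.
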